Diabetic retinopathy (DR) is a complication of diabetes and a leading cause of blindness in adults as early as age 20. Youth with type 1 and type 2 diabetes are at risk for DR, yet only 35-72% of youth undergo recommended DR screening exams, with minority youth and children from lower socioeconomic backgrounds less likely to undergo screening as compared to their white counterparts.¹

Early detection of diabetic retinopathy through screening prevents progression to vision loss. While DR screening is traditionally fulfilled by a referral to an eye care provider (ECP) for a dilated eye exam, use of nonmydriatic fundus cameras with new and innovative autonomous artificial intelligence (AI) systems have recently been developed for DR screening. Autonomous AI performed at the point-of-care (POC) provides an immediate result, and was FDA approved for use in adults in 2018.² Autonomous AI technology has been validated against patient outcome, demonstrating an 87% sensitivity and 90% specificity in detecting referable DR in adults,² compared to 30-40% sensitivity for clinical experts,³ with equal safety and effectiveness for all races, ethnicities and ages, and higher diagnostic accuracy than clinical experts for detecting DR and DME. In a pilot prospective study at our pediatric diabetes center using AI technology for DR screening, we demonstrated 85.7% sensitivity and 79.3% specificity in detecting referable diabetic retinopathy, and an improved adherence to screening from 49% to 95%.⁴

We hypothesize that POC autonomous AI in the diabetes care setting will increase DR screening rates in youth with diabetes and mitigate disparities in access to screening. In this study, we will determine if point of care autonomous AI improves screening adherence compared to standard in person eye care professional exams in a randomized control trial.

A2 Primary Hypothesis

We hypothesize that POC Autonomous AI screening will increase DR screening rates in comparison to ECP (Aim 1a), and will improve follow-up with ECP in the case of abnormal findings (Aim 1b).

A3 Purpose of the Study Protocol

We will perform a randomized control trial to determine if autonomous AI increases DR screening rates in comparison to ECP. ECP-based dilated eye exams are the standard of care, and thus will serve as the control arm in this study. Autonomous AI is an acceptable comparator, because it has been validated against patient outcome in the adult diabetes population,^{2,5} and data from a pilot study using autonomous AI off-label in pediatrics demonstrated diagnostic accuracy, and sufficient sensitivity and specificity for detection of DR in the pediatric population.⁴ The alternative strategy that we considered was telemedicine or teleretinal networks, which have been used for more than 20 years, but these systems have not been validated against patient outcome (ETDRS). Further, while reading centers have demonstrated consistent fundus image interpretation, the real-world use of networks with various trained readers (optometrists, ophthalmologists

and retina specialists) can result in variable interpretation.³ Thus we have chosen to compare autonomous AI to ECP.

B Study Objectives

B1 Primary Aim

To determine if point-of-care autonomous AI improves screening adherence compared to standard in-person eye care professional exams in a randomized control trial.

B2 Secondary Aim

To assess follow-up rates with ECP in the standard of care arm, compared to participants in the AI arm who screen positive and receive a referral to ECP for further evaluation.

C Study Design

C1 Overview of Study Design

This is a hypothesis-driven, pre-registered, prospective parallel, randomized control trial with a 1:1 allocation ratio where participants will be randomized to the standard of care or the autonomous AI arm.

The control arm is the standard of care referral to an eye care provider for a diabetic eye exam. In this study, to add *rigor, ethics* and maximum follow-up at ECP, participants in this arm will receive a scripted, brief educational intervention including the following 3 points: a) risks for complications of diabetes, b) what a DR screening exam entails and where it can be done, and c) reminder to have results faxed to their endocrine provider. We propose that this addresses the ethical concern of poor baseline completion of the diabetic eye exam amongst people with diabetes.

In the intervention arm, or autonomous AI arm, participants will undergo point of care diabetic eye exams using autonomous AI in the pediatric diabetes clinic, and will receive immediate results from autonomous AI. If the screen is normal, they have completed their screening. If the AI screen is abnormal, they will then be referred to ECP for further examination and will receive a scripted educational intervention. If the images are insufficient for interpretation, they will be referred to ECP for further examination and will receive a scripted educational intervention.

Followup: After randomization in the study, participants will have 6 months to complete the diabetic eye exam (in the control arm) or follow-up eye exam (in the intervention arm if AI abnormal). If the exam is not complete by 6 months, or the participant cannot be reached to determine completion of the exam, it will be considered not done.

C2 Subject Selection and Withdrawal

2.a Inclusion Criteria

- T1D: 11 years of age or older or in puberty, with diabetes for at least 3 years (ADA guidelines)⁶
- T2D: at diagnosis and thereafter (ADA guidelines)
- No known diabetic retinopathy
- No diabetic retinopathy exam within the last 6 months

2.a Exclusion Criteria

- Known diabetic eye disease

2.b Subject Recruitment Plans and Consent Process

Individual(s) responsible for approaching participant(s): Research coordinators

Where and when recruitment will take place:

Participants will be recruited, screened for eligibility, and consented in a private clinic/room to ensure privacy.

Consent process:

Participants will read through the consent form with the research coordinator, have time to review it and ask questions about the study and study procedures.

2.c Randomization Method and Blinding

To prevent selection bias and ensure sample size balance between the groups and sites, a stratified randomization (by site) scheme was developed with participants randomized in permuted block schedules of 4 and 6. Within each block, participants are randomized with a 1:1 allocation ratio to the control group and intervention group. This randomization sequence was created by a statistician unaffiliated with the study to ensure masking, and then another unaffiliated statistician entered the randomization scheme into REDCAP's randomization software.⁷ After consent, the research coordinator will enter the participant location, and the randomization allocation is generated. All parties are masked to the allocation until the participant is randomized, and then all parties are unmasked.

2.d Risks and Benefits

This study involves no medical risks to the participants because of the non-invasive nature and lack of use of dilating eye drops for fundus photography. The only potential risk is related to privacy issues, should data with identifiers become non-secure.

Confidentiality: There is the risk that psychological, emotional, financial, social, and legal risks might result if confidentiality cannot be maintained in this study. All study team members are HIPPA trained and will take every step to respect participants' privacy and

protect their confidentiality throughout the study. We share the information gathered in the study only with the people who need to know this information. All information gathered during this study will be kept in a secure HIPAA compliant database, REDCap.

Benefit: Undergoing diabetic eye exam screening can lead to possible detection of diabetic retinopathy and allow for appropriate timely management.

2.e Early Withdrawal of Subjects

Participants may withdraw from the study at any time by notifying the study team.

2.f When and How to Withdraw Subjects

The participant may choose to withdraw from the study. The study visit is a one-time study visit, so once the participant is enrolled, if they choose to withdraw, it will not affect study procedures. It will also not impact the course of the participant's clinical care.

2.g Data Collection and Follow-up for Withdrawn Subjects

Data collected from subjects will remain in the dataset as this is an intent to treat analysis, but no follow-up will be conducted on withdrawn subjects.

D Study Procedures

D1 Screening for Eligibility

Patients being seen in the diabetes center will be pre-screened for eligibility by the research team based on the inclusion criteria. Eligibility will be confirmed with the patient's diabetes provider at the time of the clinic visit, and with the potential participant based on the inclusion criteria. The study coordinator will confirm that the participant has not had a diabetic eye exam within the prior 6 months.

D2 Schedule of Procedures

If the patient is eligible and interested in the study, the research coordinator will meet with the patient and caregiver in an exam room for privacy and confidentiality. The research coordinator will explain the study and study procedures, read the informed consent form with the participant and caregiver, and allow time for questions on the study and consent form.

If the participant is less than 18 years of age, the parent will sign the consent form and the participant will sign the assent. If the participant is 18 years of age or over, the participant can sign the consent.

After consent is signed, a new record is entered in REDCap and the participant assigned a study ID, then the site is entered and the randomization allocation generated. Until randomization is assigned, the study coordinator and participant are masked to the

allocation. At the time of consent, 3 phone numbers are collected from the participant for future follow-up.

Participants will be randomized to one of two interventions:

- 1) **ECP + Educational Intervention.** The control arm will receive the standard of care referral to ECP for DR screening. To add rigor, ethics and maximum follow-up at ECP, participants in this arm will receive a scripted, brief educational intervention including the following 3 points: a) risks for complications of diabetes, b) what a DR screening exam entails and where it can be done, and c) reminder to have results faxed to their endocrine provider.
 - a. Participants in the control arm will complete a survey after the ECP eye exam is complete.
- 2) **Autonomous AI.** Participants in the intervention arm will undergo POC DR screening using autonomous AI in the pediatric diabetes clinic, and will receive immediate results from autonomous AI. If the screen is normal, they have completed their screening. If the AI screen is abnormal, they will then be referred to ECP for further examination and will receive a scripted educational intervention stating the importance of eye care follow-up and to have results faxed to their endocrine provider. If the images are insufficient after 3 attempts, then they will be referred for eye care follow-up.
 - a. Participants in the AI arm will complete a survey after the AI eye exam is complete.
- 3) **Follow-up:** Participants will have up to 6 months to complete the ECP diabetic eye exam (control arm) or follow-through eye exam after an abnormal AI result in the intervention arm.

Children with diabetes care are typically seen by their diabetes provider every 3 months. As part of routine diabetes intake, patients are asked if they have had an eye exam since the last visit and the date is recorded by the nurse or diabetes provider.

If a participant returns for diabetes care to the clinic within the 6-month follow-up window, and an eye exam is reported, the research coordinator will meet with the participant to complete a follow-up acceptability survey (paper and pencil or on a tablet). If the eye exam results are not in the medical chart, the research coordinator will contact the eye doctor's office to have the results faxed to the provider office.

Once the participant reaches their 6-month follow-up window and there is no documentation of the eye exam in the medical record, the study coordinator will approach the participant in person at the next diabetes clinic visit to determine if they completed an ECP visit, or contact the family by EHR-based secure messaging, or calls / voicemails to all 3 phone numbers provided upon enrollment. The eye exam will be considered complete if documentation of the eye exam is in the medical record, or the participant/caregiver reports the diabetic eye exam completed.

If the exam has not been completed by 6 months or the participant cannot be reached, it will be considered not done/unscreened.

D3 Autonomous AI diabetic eye exam procedure

In prior studies with pediatric patients,⁴ pharmacologic dilation was not required; therefore the participant's eyes will *not* be pharmacologically dilated in this study. The autonomous AI system guides the operator to acquire two color fundus images of each eye, determined to be of adequate quality using an image quality algorithm, one each centered on the fovea and the optic nerve, and guides the operator to retake any images of insufficient quality. This process requires approximately 10 minutes, after which the autonomous AI system reports one of the following results within 60 seconds: "DED present, refer to specialist", "DED not present, test again in 12 months", or "insufficient image quality". The latter response will occur if the operator is unable to obtain images of adequate quality after 3 attempts.

The IDx-DR autonomous AI system used in this study is not labeled for youth <22 years, thus all images will be overread in a deferred manner by a board certified retina specialist at the end of the study. Study procedures and follow-up are determined by the AI system results.

D4 Safety and Adverse Events

4.a Safety and Compliance Monitoring

Site investigators will monitor compliance with the protocol and good clinical practice (GCP) guidelines.

4.b Medical Monitoring for adverse events

Participants will be monitored for adverse events during the study visit and during the fundus photography.

4.c Definitions of Adverse Events

An adverse event (AE) is defined as any untoward medical occurrence in a patient or clinical investigation subject.

4.d Classification of Events

- Relationship**

Medical judgement should be used to determine the relationship, considering all relevant factors, including pattern of reaction, temporal relationship, de-challenge or re-challenge, confounding factors such as concomitant medication, concomitant diseases and relevant history.

- Severity**

The severity of the AE should be judged based on the following:

Mild: Awareness of sign(s) or symptom(s) that is/are easily tolerated

Moderate: Sufficient discomfort to cause interference with usual activity

Severe: Incapacitating or causing inability to work or to perform usual activities

4.e Data Collection Procedures for Adverse Events

All enrolled participants will be monitored for untoward incidents (e.g., “Adverse Events”) occurring during the study. The Principal Investigator (and other designated individuals, if necessary) will conduct regular monitoring for safety concerns and provide general oversight for human subject safety requirements during the study visit and fundus imaging. All adverse events that are anticipated or described in the informed consent form will be logged appropriately and reported to the IRB on at least an annual basis (e.g., at continuing review).

4.f Reporting Procedures

Any Unanticipated Problems or unexpected “Serious Adverse Events” related to the study intervention and/or test fundus imaging and affecting the risk/benefit profile of the study, will be reported to the IRB promptly, and, in all cases, within 10 business days of discovery. Unplanned and non-emergent deviations from the IRB approved protocol will be logged and reported to the IRB annually at continuing review; all planned deviations will be submitted as a Change in Research to the IRB for approval and prior to implementation. All other event reporting requirements will be followed and all necessary parties will be notified of events/problems encountered in the study and/or changes in research, in accordance with all applicable regulations and guidelines.

4.g Adverse Event Reporting Period

Any Unanticipated Problems or unexpected “Serious Adverse Events” related to the study intervention and/or test article and affecting the risk/benefit profile of the study, will be reported to the IRB promptly, and, in all cases, within 10 business days of discovery.

4.h Post-study Adverse Event

Not applicable

E. Statistical Plan

E1. Sample Size Determination and Power

The following power calculations assume 80% power and a 2-tailed type 1 error of 0.05. Data from the pilot study in pediatrics showed that of all children in the study, only 49% reported a prior diabetic eye exam, and this increased to 95% with the implementation of POC AI screening.⁴ National data show that 42% of youth with T2D and 66% of youth with T1D had a diabetic eye exam by 6 years after initial diabetes diagnosis,¹ and our preliminary data showed that of youth who met ADA criteria for DR screening, 66% had a prior diabetic eye exam (46% non-white, 85% white youth). We assume that adding the educational intervention will raise the ECP rate to 60%. Randomization and study visit occur at the same time so there is little risk of attrition, and thus the study sample size will not be expanded to account for attrition. To show difference in proportion of who gets screened we assess a 20% difference to be clinically relevant between the two

strategies. Committing to demonstrating this difference results in a sample size of 164 (n=82 ECP, n=82 AI).

E2. Interim Monitoring and Early Stopping

One interim efficiency analysis for efficacy is planned. Using the alpha spending function with O'Brien and Fleming stopping rules, we will stop the trial if we show efficacy at the $p < 0.0054$ level. To adjust for the interim look, if the trial continues to the planned full sample size, the threshold for significance will be $p < 0.0492$.

Although consideration may be given to stop the study early because of an apparent beneficial treatment effect, early termination for efficacy will be considered with caution because of the degree of uncertainty with regard to the long-term benefit of treatment even if a short-term benefit seems apparent prior to the completion of the study. This will be determined by the independent DSMB committee.

E3. Analysis Plan

Primary outcome variable.

The primary outcome is the *proportion* of participants who get screened between AI and ECP. The comparison will be assessed using a Pearson's chi-square test (primary outcome) and logistic regression (adjusting for covariates).

Secondary outcome variables.

The secondary outcome is follow-up at ECP in each arm, comparing proportion of participants who arrive at ECP for DR screening in the control arm, to the proportion of participants in the AI arm who have an abnormal AI screening, are referred to ECP for follow-up, and arrive at ECP. This will be analyzed using a Pearson's chi-square test and logistic regression (adjusting for covariates).

E3. Statistical Methods

Statistical analyses will be performed using Stata 15.1 (Statacorp, College Station, TX). The primary and secondary outcomes will be further analyzed (in addition to above) using multivariate logistic regression analyses in order to examine the relationship between demographic characteristics and the outcomes. Additionally, multivariable logistic regression analyses will assess the odds of having a previous diabetic eye exam, adjusting for known covariates associated with diabetic eye disease. This will be an intent to treat analysis; all participants will be analyzed.

E4. Missing Outcome Data

Dataset will be assessed for missing-ness and noted in results.

E5. Unblinding Procedures

Not applicable

F. Data Handling and Record Keeping

F1. Confidentiality and Security

All data for this study will be recorded and stored in REDcap through Johns Hopkins Medicine.

F2. Records Retention

Informed consent documents will be securely stored in a locked file cabinet within a locked office. Informed consents will also be scanned into the participant's electronic medical record. Eye exam results from the AI camera will be uploaded into the Media section of the participant's electronic medical record in Epic.

G. Study Administration

G1. Organization and Participating Centers

Johns Hopkins Pediatric Diabetes Center
Mount Washington Pediatric Hospital Diabetes Center

G2. Funding Source

Funding for this study is provided by the National Eye Institute of the National Institutes of Health under Award Number R01EY033233 (PI: [name]), and the Diabetes Research Connection (PI: [name]).

G3. Subject Stipends or Payments

Participants received a \$25.00 gift card, and a parking pass at the study visit.

E References

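### The specialist overread of AI images is deferred to study end, and the protocol text provided states no action when it reads an AI-normal participant as referable

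*Combined protocol and SAP*

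**What the plan says.** D3 explains that the device is off-label in this age group, "thus all images will be overread in a deferred manner by a board certified retina specialist at the end of the study". The next sentence reads: "Study procedures and follow-up are determined by the AI system results".

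D2, in line with C1, sets the path after a normal result: "If the screen is normal, they have completed their screening". The device's own message in that case is "DED not present, test again in 12 months". Referral to an eye care provider (ECP) is defined only for an abnormal or an insufficient AI result.

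Other sections bear on the point without settling it:

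- D2 on routine care: "Children with diabetes care are typically seen by their diabetes provider every 3 months". At those visits families are asked whether an eye exam has taken place.
- D4 4.e: "All enrolled participants will be monitored for untoward incidents". 4.b places monitoring at the study visit and the photography, and 4.h marks post-study events as not applicable.
- D4 4.f: "all necessary parties will be notified of events/problems encountered in the study". It names no overread trigger, recipient or referral.
- F2: "Eye exam results from the AI camera will be uploaded into the Media section" of the medical record. Nothing says where the overread is filed.
- C2 2.d names privacy as the sole potential risk. A1 reports 85.7% sensitivity and 79.3% specificity for the AI in the pediatric pilot.

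**The concern.** The protocol's reason for the overread is that the device is unlabelled for these participants, so the read looks like a safeguard. Its timing stops it from acting as one while the study runs, and no step is attached to it afterwards. A child whose AI screen was normal, and whose images the study's own specialist later reads as referable, has been told that screening is complete. Nothing in the text provided says who tells the family, how soon, or whether a referral follows. With pilot sensitivity below 100%, such a case is foreseeable, yet 2.d does not list a false-negative result.

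At stake is timely care for a small number of participants. AI-abnormal and ungradable participants already go to ECP, so the gap concerns AI-normal participants only.

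**Working it through.** **Size of the AI arm.** E1 gives 164 participants, 82 per arm, for 60% against 80%, two-sided alpha 0.05 and 80% power. The usual two-proportion formula without continuity correction gives [1.960·√(2·0.7·0.3) + 0.842·√(0.24 + 0.16)]² / 0.2² = 81.2, rounded up to 82 per arm. The figure reproduces, and 82 is used below.

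**Inputs.** Sensitivity 0.857 and specificity 0.793 are the pilot figures in A1. The documents give no prevalence of referable disease for this population (known retinopathy is excluded), so 1%, 5% and 20% are assumed. The overread's sensitivity and false-positive rate are also assumed. The low sensitivity values of 30% and 40% are those A1 quotes for clinical experts; whether they apply to this reader is unknown. All 82 are taken as gradable; ungradable sets would lower every count in proportion.

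**Formulas**, with p for prevalence:

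- Missed by the AI = 82 · p · (1 − 0.857)
- Chance of at least one miss = 1 − (1 − 0.143p)^82
- Recovered = missed × overread sensitivity (reader and AI errors taken as independent)
- AI-normal sets = 82 · [(1 − p) · 0.793 + 0.143p]
- False overread referrals = 82 · (1 − p) · 0.793 × false-positive rate

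| | p = 1% | p = 5% | p = 20% |
|---|---|---|---|
| Missed by the AI | 0.12 | 0.59 | 2.35 |
| Chance of at least one | 11% | 44% | 91% |
| Recovered, sensitivity 30% | 0.04 | 0.18 | 0.70 |
| Recovered, sensitivity 40% | 0.05 | 0.23 | 0.94 |
| Recovered, perfect reader | 0.12 | 0.59 | 2.35 |
| AI-normal sets | 64.5 | 62.4 | 54.4 |
| False referrals, 5% rate | 3.2 | 3.1 | 2.6 |
| False referrals, 10% rate | 6.4 | 6.2 | 5.2 |

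At p = 5% and a 5% false-positive rate there are about 3.1 / 0.59 ≈ 5 false referrals per true one with a perfect reader, and 3.1 / 0.23 ≈ 13 at 40% sensitivity. With no false positives the problem disappears.

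**Time from imaging to overread.** Neither the recruitment period R nor study end is defined. With uniform accrual and no early stop, the mean wait is R/2 if study end is the last imaging visit, and R/2 + 6 months if it is the last 6-month follow-up. For assumed R of 6, 12 and 24 months this gives 3, 6 and 12 months, or 9, 12 and 18 months. Stopping at the interim analysis (E2) would shorten it.

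**The case against.** The strongest reply is that the deferral is deliberate. The trial tests an autonomous pathway, A3 defends it with adult validation and pediatric pilot data, and A1 puts clinical experts at 30–40% sensitivity. On those figures the plan need not treat a human read as the better test, and an active human backstop is partly a design preference. This stands as far as it goes: the AI may be the better screening route overall. It does not explain why a referable finding, once the study's specialist has made it, should have no stated consequence.

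A second reply is that the benefit may be small and the false referrals more numerous. This also stands. The reader sees the same undilated images as the AI, so their errors may be correlated and recovery may fall below the table's figures.

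A third is that a promise to share such findings would naturally sit in the consent form. Those pages are not available, so the point can be made only about the protocol text provided.

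A reader might infer that a missed case has no route to care at all. The documents do not support that: the retest message and routine diabetes visits remain, although neither depends on the overread and the visits do not re-examine the retina. Nor are the waits above delays to care. They end at the overread, and for those who follow the retest message the delay is limited to about 12 months.

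**Conclusion.** The point holds as a participant-safety gap in the protocol text provided. D3 sets a specialist check because of off-label use, postpones it to study end, and ties follow-up to the AI result. No section available states an action for an AI-normal set read as referable.

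The expected number is small: 0.1 to 0.6 missed cases at 1–5% prevalence and up to 2.3 at 20%, of which the overread recovers all or fewer. These figures rest on the pilot sensitivity and on an assumed prevalence. The delay to care cannot be fixed from the documents.

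A reader might also infer that the trial's result is at risk. It is not: an AI-normal participant counts as screened whatever the overread says, and the analysis plan does not use the overread. The change is worth making because it is cheap, with medium confidence in its value given the small and uncertain yield.

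**What to change.** **In D3:**

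- Have the same specialist read the AI-arm sets on a rolling basis, masked to the AI result, with a stated turnaround (for example about 30 days, which is a suggestion and not a figure in the plan).
- Have a coordinator, not the reader, compare the overread with the AI result.
- When an AI-normal set is read as referable, promptly notify the participant or caregiver and the diabetes provider, refer to ECP, and file the overread in the medical record.
- If earlier reading is not possible, add at least the notification and referral rule.

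**In E3:** state that these participants remain screened in the primary outcome, fall outside the secondary denominator (abnormal AI screens), and are reported separately. Limiting the rule to AI-normal sets leaves the secondary outcome undisturbed.

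**In 2.d:** list a false-negative result beside privacy.

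Notifying withdrawn participants is optional. 2.g rules out follow-up for them, so it would need an IRB-approved change.

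**Cost:** at most 82 sets, already due to be read, are read sooner. There are also a few calls and referrals, including about 3 to 6 false ones at an assumed 5–10% false-positive rate. A human check would then run beside the autonomous pathway, but it enters neither outcome. The tests and the sample size of 164 do not change.

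### E2 gives two incompatible rules for stopping on efficacy and plans no adjusted estimate if the trial stops early

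*Combined protocol and SAP*

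**What the plan says.** E2 plans one interim efficacy analysis with O'Brien-Fleming stopping. Its first paragraph is firm: "we will stop the trial if we show efficacy at the" p<0.0054 level, with p<0.0492 at the end if the trial runs to full size. Its second paragraph is not: "early termination for efficacy will be considered with caution because of the degree of uncertainty with regard to the long-term benefit of treatment", with the decision left to an independent DSMB. E2 does not say when the look takes place, whether enrolment pauses for it, or how the effect would be estimated after a stop.

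E1 sets the size: "The following power calculations assume 80% power and a 2-tailed type 1 error of 0.05"; "We assume that adding the educational intervention will raise the ECP rate to 60" percent; "we assess a 20% difference to be clinically relevant between the two" strategies; giving a "sample size of 164 (n=82 ECP, n=82 AI"). E1 also reports the pilot, where 49% had a prior exam and "this increased to 95% with the implementation of POC AI screening".

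E3 analyses the primary outcome by Pearson chi-square and logistic regression, by intention to treat, with all participants analysed. C1 and D2 give each participant a 6-month window. A2 adds the hypothesis that AI screening "will improve follow-up with ECP in the case of abnormal findings (Aim 1b"), which E3 treats as a secondary outcome restricted, in the AI arm, to participants with an abnormal screen.

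**The concern.** A DSMB whose interim p-value is 0.004 could not tell from E2 whether it must stop or may continue. The reason given for caution does not help it decide. It concerns long-term benefit, and the outcome window ends at 6 months whether or not the trial continues.

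The second matter is the estimate. A trial that stops because an interim difference was large reports, on average, a difference larger than the truth. At 41 per arm the difference needed to cross is well above the 20 points the trial is sized for. The plan would report it with the ordinary chi-square and logistic results, with no adjusted estimate or interval. Services deciding whether to adopt AI screening will read the size of the gain as well as the p-value.

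**Working it through.** **Inputs.** From E1: control 60%, difference 20 points, two-sided alpha 0.05, power 80%, 82 per arm. From E2: interim p<0.0054 (z = 2.782) and final p<0.0492. From E3: uncorrected Pearson chi-square. Assumed: a look at 41 per arm, because E2 gives no time. The interim level is close to 0.0052, the first-look level of the classical two-look O'Brien-Fleming design at half information. Looks from one third to three quarters are shown as a range.

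**The plan's own figure.** n per arm = [1.96 × √(2 × 0.7 × 0.3) + 0.842 × √(0.6 × 0.4 + 0.8 × 0.2)]² / 0.2² = (1.270 + 0.532)² / 0.04 = 81.2, so 82 per arm and 164 in all. E1 is reproduced.

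**Chance of crossing, 41 per arm, 60% v 80%.** By normal approximation the critical difference is 2.782 × √(2 × 0.7 × 0.3 / 41) = 0.282. The standard error under the alternative is √(0.40 / 41) = 0.0988. The chance is Φ((0.20 − 0.282) / 0.0988) = 20.4%. Exact binomial enumeration, counting crossings in favour of AI, gives 21.5%.

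**Smallest difference that crosses.** With 25/41 controls screened (61.0%), AI needs 36/41, a difference of 11/41 = 26.8 points. With 24/41 (58.5%), AI again needs 36/41, a difference of 12/41 = 29.3 points. With an observed control rate near 60%, every crossing therefore exceeds 20 points.

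**Exact results by look time:**

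| Look, per arm | Crosses, 60% v 80% | Mean difference if crossed (truth 20) | Crosses, 60% v 95% | Mean difference if crossed (truth 35) |
|---|---|---|---|---|
| 27 (about 1/3) | 11% | 40.2 | 69% | 40.0 |
| 41 (1/2) | 22% | 33.2 | 91% | 36.5 |
| 55 (about 2/3) | 31% | 29.6 | 98% | 35.4 |
| 62 (about 3/4) | 36% | 28.3 | 99% | 35.2 |

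**Averaged over stopping and continuing (simulation, halfway look, binding stop).** At a true 20 points: 0.215 × 33.2 + 0.785 × 18.2 = 21.4. At a true 35: 0.910 × 36.5 + 0.090 × 27.6 = 35.7. The unconditional bias is about 1.4 and 0.7 points.

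**Participants already enrolled at the look.** If the look waits for 82 participants with 6-month outcomes and enrolment runs evenly over A months, the number enrolled is about 82 + 164 × 6/A: 109 for A = 36, 123 for A = 24, 137 for A = 18, 164 for A = 12. A is assumed; the documents give no accrual rate. The later participants are not selected by the interim result. With m of them per arm and a true 20 points, the expected estimate after a crossing becomes (41 × 33.2 + m × 20) / (41 + m). For m = 13.7, 20.5, 27.3 and 41 this is 29.9, 28.8, 27.9 and 26.6 points.

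**Type I error of a non-binding boundary.** A false claim needs either a crossing at the look or p<0.0492 at the end. The probability of that union is the same whether or not the DSMB stops, so allowing it to continue cannot raise the error.

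**The case against.** The two paragraphs can be read together: the first gives the boundary, the second gives the DSMB the judgement. That is common practice and may be what is meant. But the first paragraph says the trial will stop, so the intended reading has to be written down.

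It can also be said that conditional overstatement comes with any efficacy stop, that it arises in about one trial in five at the planned rates, and that the average over all outcomes is only 21.4 against 20. This is correct and limits the weight of the point. It does not help the reader of a trial that did stop.

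Three stronger readings are tempting, and the documents do not support them.

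- A reader might infer that the trial will stop about nine times in ten. That pairs the assumed 60% control rate with the pilot's 95%. E1 pairs 95% with 49% and sizes the trial on 60% plus 20 points. The 91% also needs a halfway look, and it is the chance of crossing, which equals stopping only under the firm reading of E2.
- A reader might infer that a stop halves the data for Aim 1b. That is the worst case, with enrolment paused at 82. Pilot sensitivity 85.7% and specificity 79.3%, with an assumed prevalence of 3% to 10%, give 0.857 × prevalence + 0.207 × (1 − prevalence) = 23% to 27% abnormal: 19 to 22 of 82, or 9 to 11 of 41. With 109 to 137 already enrolled and 25% abnormal, there would be about 14 to 17; with all 164 enrolled, nothing is lost. Even in the worst case, at an assumed 60% v 90% follow-up, the 95% half-width goes from about 17 points (82 v 20) to 24 (41 v 10).
- A reader might conclude that enrolment should run to 164 after a crossing. That gives up the saving for which the look was planned. It is a trade-off for the sponsor, not a correction.

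**Conclusion.** The conflict in E2 is certain and needs no assumption: one paragraph is mandatory, the other discretionary. The missing plan for estimation is also plain from the text. Its size depends on the look time and the true rates. At the sizing rates a halfway look crosses about 22% of the time, and the mean observed difference is then about 33 points against 20, or 40 to 28 points for looks from one third to three quarters. At 60% v 95% crossing is likely, but the overstatement is small at halfway (36.5 v 35) and later; it is about 5 points only for a look at one third. Frequent crossing and large overstatement therefore belong largely to different scenarios. The validity of the primary test does not turn on this point. It is a cheap improvement to the rule and to the reported effect.

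**What to change.** 1. Rewrite E2 as one rule. Say either that crossing p<0.0054 stops the trial, or that it is a non-binding guideline for the DSMB. State when the look takes place and whether enrolment continues while 6-month outcomes mature.

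2. After any early stop, report a median-unbiased difference with a stage-wise group-sequential confidence interval beside the ordinary estimate. One technical caution: for a stop at the first look with no later data, stage-wise ordering returns the ordinary estimate and interval. The SAP should therefore say how data arriving after the look enter the calculation, and add a bias-adjusted estimate for the case with none. That adjustment is modest, in line with the unconditional bias of about 1 to 1.5 points shown above, so the report should also say that the trial stopped early.

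3. Confirm in E2 that everyone randomised before a stop is followed to 6 months and included in the final primary and Aim 1b analyses. C1, D2 and E3 largely imply this, but E2 does not say it for a stopped trial. On the figures above, this alone brings the expected estimate from 33 down to between 30 and 27 points.

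The cost is protocol and SAP wording, a little more analysis work and a slightly less favourable reported effect. No participants are added.
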